12.0 Statistical Considerations

We will enroll 95 children in order to target 40 completers ($n = 20/\text{group}$, allowing for 15-20% screen fail and 15-20% attrition). Attrition (apart from screen fails) will occur between the two scanning visits, which are only one week apart and are expected to be due to noncompliance or in-scanner subject motion that renders data unusable. Attrition rates are not expected to

change from year to year, as subjects will remain active only from the time of screening to Visit 3 (up to 8 weeks).

In similar research, pre/post correlations of 0.72 and 0.89 were found for measures of Theory of Mind (closely related to social perspective taking) in a VR intervention for social cognition training.⁵⁰ In research by co-I [name] involving a multi-session skill-building intervention,⁵¹ pre/post scores had a correlation of 0.69 on the Perspective Taking subscale of the Interpersonal Reactivity Index. Here, we use a more conservative estimate for a pre/post correlation of social perspective taking of 0.6. With 20 subjects per group and assuming an ANCOVA model (specified below) is used with a pre/post correlation for social perspective taking of 0.6 an effect size of 0.73 (observed for the meanness rating in the preliminary study) can be detected between two groups with 80% power using a two-sided two-sample t-test with alpha level of 0.05.

For each primary outcome measure, a separate linear mixed model will be employed to determine predictors of post-treatment scores, with pre-treatment scores, condition, time, group, and a time-by-condition interaction term as regressors. Time-by-condition is a regressor to account for potential improvements in perspective taking with treatment (since there are two conflict scenarios presented). From this model, using appropriate contrast statements we can both test for the primary endpoint (change at end of Scenario 3) and examine trends over time between the three groups. We will also conduct with fMRI data a 2x3 (pain perspective condition by group) within-subjects ANOVA on data from each ROI.

Across the entire sample, we will calculate the correlation of IRI Perspective Taking with our pre-treatment VR Perspective Taking and AOP scales, to further validate these measures. Similarly, we will assess the relationship between target engagement measures with VC Intentions and Real-life Responses. Exploratory regression analyses will also examine whether target engagement measures are associated with age, sex (to address sex as a biological variable), IQ, task completion, mood, callous-unemotional traits, past experience with video games or VR, or Environmental Presence (each variable examined separately due to the small sample sizes). Finally, we will conduct whole-brain fMRI analysis (2x3 pain perspective condition-by-group ANOVA), in order to identify neural changes in areas outside our primary ROIs (cluster-corrected $p < .05$).

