This is an fMRI measure of brain function while imagining pain happening to oneself or the virtual counterpart. Following standard preprocessing of fMRI data, we will calculate the regression coefficient for each stimulus type (Self Pain; Self No Pain; Other Pain; Other No Pain). We will extract mean activity from a priori regions-of-interest (ROIs), established as 10-mm radius spheres around MNI coordinate peaks in dACC (-2,33,40) and anterior insula (left: -40,22,0; right: 39,23,-4), which were identified as key regions for pain response in a recent meta-analysis. Brain activity will be quantified by contrasting self-perspective pain (Self Pain vs. Self No Pain) with other-perspective pain (Other Pain vs. Other No Pain). Cohen's d effect size will be calculated separately for each treatment and each ROI. For more traditional statistical measures, a 2x3 (pain perspective condition by group) within-subjects ANOVA test will be performed on data from each ROI.

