5.0 Study Design

This project will examine how levels of a virtual reality treatment that provides users with the alternate perspective of an interpersonal interaction impacts psychological and neurobiological markers of perspective taking. Prior to Visit 3, participants will be randomly assigned to different VR perspective conditions, stratified by sex, presence/absence of ADHD diagnosis, and ODD/CD diagnosis, via an a priori randomization chart. An equal number of youth will be randomly assigned to either the alternate perspective condition or control condition. Assignment will be sealed for the experimenter until immediately prior to Visit 3 (for visit preparation, experimenter must be unblinded). Visits 1 and 2 will be identical for both groups. At Visit 3, the initial VR scenarios and assessments will be identical. The participant will then re-experience the VR scenarios depending on their assigned condition. Additional VR assessments and the MRI scan will be identical for both groups.

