Participants will be instructed that if they need to contact the study team on the day of their study visit (e.g., if they are running late), to call or text us via our Google Voice number, which can be connected to our lab tablets.

For Visit 3, we will remind parents of the information they completed on the Medication Log (see Visit 2 Study Procedures), as it would be helpful for the same medications to be used at that visit. However, we will caution that they should use their best judgement and follow doctor's orders when providing medication, and that this is not a study requirement.

Randomization will occur only for those participants that meet all inclusion/exclusion criteria following the first study visit and are able to be scheduled. A randomization table will be created by our statistical team, stratified by sex, ADHD status, and ODD/CD diagnosis to create equal numbers of boys and girls in each condition. This assignment will be sealed to the research team until within 24 hours of the third study visit.

Previously active subjects whose visits were cancelled due to the COVID-19 outbreak will be permitted to restart all study procedures, including being reconsented using the most recent informed consent documents.

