11.0 Study Withdrawal/Discontinuation

A child participant or their parent may withdraw from the study at any time by letting the research team know they wish to discontinue their participation. The participant(s) will be paid for their time completed in the study.

Participants will be precluded from continuing the intervention if they report adverse health consequences from using virtual reality equipment during practice or intervention. In addition, inability to complete the MRI scan, including claustrophobia or an unforeseen health consequence, will also halt a subject's participation.

If a worsening of DBD symptoms is identified via voluntary report or visit assessments, the family will be queried to determine the nature of symptoms, including relationship and proximity to study procedures. [name] and clinical psychologists on the team will review these data, and if a worsening of symptoms is judged to be significant and likely related to study participation, the subject will be discontinued from participation. Additionally, depending on the severity of symptoms, the subject may be offered or referred for further evaluation of symptoms; the urgency of this evaluation will depend on the nature and severity of symptoms but may range from a standard outpatient visit to an urgent/emergent evaluation.

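### Enrolling 95 children does not fit 40 completers at the stated loss rates: 95 would give about 61–69 completers, and 40 completers need only about 56–63 enrolled

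*Combined protocol and SAP*

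**What the plan says.** Section 12.0 (Statistical Considerations) sets the sample size: "We will enroll 95 children in order to target 40 completers", which is 20 per group, "allowing for 15-20% screen fail and 15-20% attrition". It treats the two losses as separate: "Attrition (apart from screen fails) will occur between the two scanning visits", and it puts the second down to noncompliance or to motion that spoils the scan. The same section bases its power statement on 20 per group, an effect size of 0.73, a pre/post correlation of 0.6, a two-sided alpha of 0.05 and 80% power.

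Two other sections name ways of leaving the study, without figures. Section 6.0: "Randomization will occur only for those participants that meet all inclusion/exclusion criteria following the first study visit and are able to be scheduled". Section 11.0 ends participation for "inability to complete the MRI scan, including claustrophobia or an unforeseen health consequence".

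The design has two arms. Section 5.0: "An equal number of youth will be randomly assigned to either the alternate perspective condition or control condition". Some analysis text still assumes three. Section 12.0 plans to "examine trends over time between the three groups", and Section 3.0 says "a 2x3 (pain perspective condition by group) within-subjects ANOVA test will be performed on data from each ROI". Section 12.0 repeats the 2x3 layout for the region-of-interest and whole-brain analyses.

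**The concern.** An enrolment target should follow from the completers wanted and the losses expected. Two losses of 15–20% each leave roughly two thirds of those enrolled, yet 40 of 95 is 42%. At least one of the three figures must be wrong or incomplete.

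What is at stake depends on which one. If the loss rates are right, the trial enrols more children with disruptive behavior disorders than its power statement calls for, and many of the extra children would go on to MRI visits with about an hour of scanning each. If 95 and 40 are right, more than half of the enrolled children are expected not to finish, and the stated rates do not say so. Sections 10.0 and following have staff compare enrolment with its targets every week and put accrual and retention under monitoring, so a wrong target or a wrong loss rate carries through to that oversight.

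**Working it through.** **Inputs.** All from Section 12.0: enrolment 95; completers 40 (20 per group); screen failure s = 15–20%; attrition a = 15–20%; effect size d = 0.73; pre/post correlation r = 0.6; two-sided alpha 0.05. Two equal arms, from Section 5.0.

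**1. The plan's power figure.** Two-sample t-test (noncentral t), with the SD scaled for ANCOVA by √(1 − 0.6²) = 0.8. With 20 per arm, power for d = 0.73 is 80.3%, and the effect detectable with 80% power is 0.727. The plan's figure reproduces, so 20 per group is sound on its own terms.

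**2. Completers from 95.** Losses in sequence: 95 × (1 − s) × (1 − a).
- 20% and 20%: 95 × 0.80 × 0.80 = 60.8
- 15% and 20%: 95 × 0.85 × 0.80 = 64.6
- 15% and 15%: 95 × 0.85 × 0.85 = 68.6

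That is 1.52 to 1.72 times the stated 40 (60.8/40 and 68.6/40).

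**3. Enrolment needed for 40.** 40 / [(1 − s)(1 − a)].
- 15% and 15%: 40/0.7225 = 55.4, so 56
- 20% and 20%: 40/0.64 = 62.5, so 63

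**4. Other readings.**

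| Reading | Completers from 95 | Enrolment for 40 |
|---|---|---|
| Losses in sequence | 60.8–68.6 | 56–63 |
| Losses added | 95 × 0.60 = 57.0 to 95 × 0.70 = 66.5 | 40/0.70 = 57.1 to 40/0.60 = 66.7, so 58–67 |
| Mistaken inflation, 40 × (1 + s)(1 + a) | – | 52.9–57.6, so 53–58 |
| Screen failures not counted as enrolled | 95 × 0.80 = 76 to 95 × 0.85 = 80.8 | 40/0.85 = 47.1 to 40/0.80 = 50, so 48–50 |

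None gives 95 for 40.

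**5. Loss implied by 95 and 40.**
- Total: 1 − 40/95 = 57.9%. The stated rates give 1 − 0.7225 = 27.75% to 1 − 0.64 = 36%.
- Attrition, if screen failure is 20%: 1 − 40/76 = 47.4%. If it is 15%: 1 − 40/80.75 = 50.5%.
- Further uncounted loss, if both stated rates hold: 1 − 40/60.8 = 34.2% to 1 − 40/68.6 = 41.7% of the expected completers.

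**6. Consequences if the stated rates hold.**
- Excess enrolment: 95 − 63 = 32 to 95 − 56 = 39 children. Of these, 32 × 0.80 = 25.6 to 39 × 0.85 = 33.2 would pass screening.
- With 30 to 34 per arm, the detectable effect is 0.588 to 0.552, and power for 0.73 is 93.5% to 96.0%.

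**7. A possible origin (inference only).** Three arms of 20 make 60 completers, which need 60/0.64 = 93.75, so 94, at 20% and 20%. At 15% and 15% they need 60/0.7225 = 83.0, rounded up to 84. The first is close to 95, and three-group wording remains in the text. The documents describe no third arm, and the finding does not rest on this.

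**The case against.** The best defence is that the two stated rates do not cover every loss. Section 12.0 confines attrition to the interval between the two scans, so a child lost after screening but before or at the Visit 2 scan falls outside it. Section 6.0 also requires that a child can be scheduled, and it lets children whose visits were cancelled because of COVID-19 restart with new consent; these may be among the 95. Section 11.0 adds children who cannot complete a scan or who report adverse effects from the VR equipment. On this view 95 may be realistic and the fault is only an incomplete list of losses.

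Part of this stands. Understated losses are a real possibility, so the surplus of children is conditional, and the 26–33 who would go on to scans assumes that no other loss intervenes. It also means that cutting enrolment without checking could hurt the trial. If the true loss is 58%, enrolling 56–63 would give 56 × 40/95 = 23.6 to 63 × 40/95 = 26.5 completers, about 12–13 per arm, with power for 0.73 of about 57–61%.

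It does not rescue the sentence. None of these losses has a figure, and together they would have to remove a further 34–42% of expected completers, as much as or more than the two stated losses combined.

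It is also fair to say that the mismatch leaves the test, alpha, allocation and power untouched, and that the three-group wording is a separate defect: correcting it does not correct the enrolment figure.

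**Conclusion.** The concern holds. On the plan's own loss rates, 95 enrolled corresponds to about 61–69 completers, 52–72% more than the stated 40, and 40 completers correspond to 56–63 enrolled. The result does not depend on whether the losses are multiplied or added. It assumes only that the two stated rates are the expected losses, and the documents give no others.

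The documents do not show which figure is wrong. The 20-per-group power statement reproduces, so the fault lies in the enrolment number or in the loss rates. Power is not reduced as long as 40 children complete.

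**What to change.** Rewrite the enrolment sentence in Section 12.0 so that its figures agree. The sponsor should first establish what losses it actually expects, and then take one of three routes:

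- **Keep 95 and 40.** State the expected loss at each stage, including categories not now counted, such as children who cannot be scheduled or do not complete the Visit 2 scan. The total must come to about 58%.
- **Keep 40 and the stated rates.** Set enrolment at about 56–63. This lowers the target by 34–41% (1 − 63/95 to 1 − 56/95) and is safe only if the stated rates cover all losses.
- **Keep 95 and the stated rates.** Restate completers as about 61–69 (30–34 per arm), with a detectable effect of about 0.55–0.59.

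In the same edit, align the three-group wording and the 2x3 condition-by-group analyses in Sections 3.0 and 12.0 with the two-arm design.

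The cost is one corrected sentence and a few wording changes. No route needs more children than are now planned.

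### Randomisation is stratified by sex, ADHD and ODD/CD diagnosis, but the primary model omits all three; if they are prognostic, the test is conservative and gives up power

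*Combined protocol and SAP*

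**What the plan says.** Section 5.0 assigns children 1:1, "stratified by sex, presence/absence of ADHD diagnosis, and ODD/CD diagnosis, via an a priori randomization chart". Section 6.0 repeats this: the table is to be "stratified by sex, ADHD status, and ODD/CD diagnosis to create equal numbers of boys and girls in each condition".

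Section 12.0 gives one linear mixed model for each primary outcome, "with pre-treatment scores, condition, time, group, and a time-by-condition interaction term as regressors". None of the three factors is named. Later in that section, sex appears once, in exploratory regressions on "whether target engagement measures are associated with age, sex (to address sex as a biological variable), IQ, task completion, mood" and other variables, each examined separately. ADHD status and ODD/CD diagnosis enter no analysis. No reason is given for leaving the factors out, and no adjusted sensitivity analysis is planned.

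The regressor called group is not defined. The arm is already present as condition, and section 12.0 otherwise uses group for treatment groups, so it is unlikely to mean the strata.

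**The concern.** Stratified allocation keeps the arms nearly balanced on the three factors. If a factor predicts the post-treatment score beyond the pre-treatment score, that balance reduces the true variance of the arm difference. A model without the factor does not see the reduction: it counts the factor's contribution as noise, so its standard error is too large and its true type I error falls below 5%.

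The precision bought by stratifying is then mostly not used in the test. With 20 per arm and power planned at 80%, a few points of power are worth having. If no factor is prognostic, the standard error is correct and nothing is lost.

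**Working it through.** **Inputs from section 12.0.** 20 completers per arm, effect size 0.73, two-sided alpha 0.05, attrition 15–20%, and the pre/post correlation ("we use a more conservative estimate for a pre/post correlation of social perspective taking of 0.6").

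**Assumed, because the documents do not give it.** R², the share of post-score variance left after baseline adjustment that the three factors explain, is taken from 0 to 0.30. Each factor is treated as binary (8 strata). Block size is also not stated.

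**Step 1: the plan's own figure.** Residual SD = √(1 − 0.6²) = 0.80. Standardised effect = 0.73/0.80 = 0.9125. Noncentrality = 0.9125 × √(20/2) = 2.886. Power is 80.3% with 38 degrees of freedom and 80.2% with the 37 of an ANCOVA. The stated 80% is reproduced.

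**Step 2: ideal power after adjustment.** Residual SD becomes 0.80 × √(1 − R²), with 37 − 3 = 34 degrees of freedom. Power is 80.1%, 82.0%, 84.0%, 88.0% and 91.8% at R² = 0, 0.05, 0.10, 0.20 and 0.30. This assumes perfect balance on all covariates, so it is an upper guide.

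**Step 3: simulation.** Post score = 0.6 × pre score + three binary factors with equal contributions + error + 0.73 × arm. Each trial was analysed by ANCOVA on arm and pre score, without and with the three main effects; 10,000 null and 10,000 alternative trials per setting.

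- Design A: blocks of 2, 40 randomised and analysed, factor prevalences 0.5.
- Design B: blocks of 4, 50 randomised, 40 analysed (20% attrition), prevalences 0.5.
- Design C: as B, with prevalences 0.5, 0.7 and 0.3.

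| R² | Type I error, planned model (A / B / C) | Mean SE ÷ true SD, planned model (A / B / C) | Power %, planned → adjusted: A | B | C |
|---|---|---|---|---|---|
| 0 | 0.049 / 0.049 / 0.047 | 1.00 / 0.99 / 1.00 | 78.5 → 78.0 | 78.9 → 77.7 | 78.4 → 76.7 |
| 0.05 | 0.045 / 0.046 / 0.049 | 1.01 / 1.01 / 0.99 | 80.0 → 80.7 | 78.7 → 79.6 | 79.0 → 79.0 |
| 0.10 | 0.045 / 0.044 / 0.043 | 1.03 / 1.02 / 1.03 | 79.9 → 82.4 | 80.2 → 82.3 | 79.7 → 81.2 |
| 0.20 | 0.032 / 0.034 / 0.035 | 1.09 / 1.07 / 1.07 | 81.7 → 86.9 | 80.1 → 85.6 | 80.3 → 85.8 |
| 0.30 | 0.026 / 0.032 / 0.029 | 1.16 / 1.11 / 1.11 | 82.3 → 90.7 | 81.1 → 90.0 | 81.7 → 90.2 |

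The adjusted model's type I error stayed between 0.047 and 0.054 throughout.

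**Step 4: is stratification the cause?** In a separate simulation with unstratified allocation (8,000 trials per setting; R² = 0, 0.10, 0.20 and 0.30), the planned model held its level, at 0.047 to 0.052. With stratified blocks of 4 and no loss, its type I error fell to 0.036 at R² = 0.20 and 0.028 at 0.30. The conservatism therefore comes from stratifying without adjusting.

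**Step 5: does it carry over to repeated measures?** A random-intercept model was simulated with three post-intervention scores and the contrast at Scenario 3. It used blocks of 4, 50 randomised and 40 analysed, an assumed within-child correlation of 0.6, assumed prevalences 0.5/0.6/0.3, and 4,000 trials per setting. Power, unadjusted then adjusted, was 80.6% and 79.9% at R² = 0, 80.4% and 82.6% at 0.10, 82.2% and 87.8% at 0.20, and 82.4% and 91.4% at 0.30. Unadjusted type I error at those four values was 0.048, 0.046, 0.038 and 0.030. The pattern is the same.

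**The case against.** The strongest reply is that no error has been shown: the test is valid, the planned power is reproduced, and the benefit depends on an R² that nobody knows. Sex and diagnosis are stable, and the pre and post scores come from the same scale, scenarios and visit, so the baseline score may already carry most of their effect. A true R² of 5% or less is quite possible, and adjustment then gains almost nothing. This stands, and it limits the weight of the point.

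The correlation of 0.6 is also the plan's cautious choice. By the Step 2 formulas, the correlations it cites of 0.69, 0.72 and 0.89 give unadjusted power of about 87%, 90% and over 99%. The ideal gain at R² = 0.10 is then about 3, 3 and 0 points, against about 4 at 0.6. This also stands.

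Third, section 3.0 computes Cohen's d from raw mean change scores, so covariates would alter the model-based test and interval but not that d.

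Finally, group might be meant as a stratum term. Section 12.0's other uses of the word make that unlikely, but only a definition would settle it.

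None of this removes the mismatch between allocation and analysis. It makes the point an inexpensive improvement and not a correction of an error.

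**Conclusion.** The concern holds. The three randomisation factors are absent from the primary model. If they are prognostic beyond baseline, the planned test is conservative and an adjusted model is more powerful.

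The size depends on the assumed R². At 10% the planned model's standard error is about 2–3% too large and adjustment gains 1.5 to 2.5 points of power. At 20% the figures are 7–9% and about 5 points; at 30%, 11–16% and 8 to 9 points. Near 5% there is little to choose between the models. At zero, adjustment loses 0.5 to 1.7 points.

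These figures rest on binary factors, permuted blocks of 2 or 4 within strata, loss unrelated to the factors, a correlation of 0.6 and an effect of 0.73. The fMRI region-of-interest analysis was not simulated. The issue is efficiency only; the planned test does not exceed its nominal 5% level because of it.

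**What to change.** In section 12.0, prespecify sex, ADHD status (yes/no) and ODD/CD stratum, each as used at randomisation, as main-effect covariates in the primary models for the VR Perspective Taking Scale and the Acknowledgement of Other Perspective Scale. Keep children with Other Specified or Unspecified diagnoses, whom section 4.1 admits, in the stratum used to randomise them. In the same sentence, define group or delete it.

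The same covariates could be added to the child-level self-versus-other contrast in each brain region. The gain there is not quantified and exists only if a factor alters that contrast.

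The cost is one sentence and three of 37 residual degrees of freedom, which in the ANCOVA simulations was at most about 1.7 points of power if the factors are not prognostic. No new data are needed: sex and the diagnoses are recorded at Visit 1. Fixing the covariates in advance also prevents a later choice between adjusted and unadjusted results.

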3.0 Outcome Measures

Primary Outcome Measure: VR Perspective Taking Scale

This scale measures the degree to which participants understand the perspective of their virtual counterpart. It will be completed after each VR scenario, both pre- and post-intervention. Each participant's change score will be as Post-treatment (Endpoint; following all VR) vs. Pre-treatment (Baseline; after first scenario). The Cohen's d effect size will be calculated using the difference in mean change scores between treatment and control conditions (e.g., $[\text{Mean}_{\text{Enriched Post-Pre}} - \text{Mean}_{\text{Control Post-Pre}}] / \text{SD}_{\text{pooled}}$), resulting in an effect size measurements for both scales with each treatment condition.

Primary Outcome Measure: Acknowledgement of Other Perspective Scale

This scale allows participants to rate the relative importance of the virtual counterpart's perspective with a scenario-specific question. It will be completed after each VR scenario, both pre- and post-intervention. Each participant's change score will be as Post-treatment (Endpoint; following all VR) vs. Pre-treatment (Baseline; after first scenario). The Cohen's d effect size will be calculated using the difference in mean change scores between treatment and control conditions (e.g., $[\text{Mean}_{\text{Enriched Post-Pre}} - \text{Mean}_{\text{Control Post-Pre}}] / \text{SD}_{\text{pooled}}$), resulting in an effect size measurements for both scales with each treatment condition.

Primary Outcome Measure: Neural response to Self vs. Other Pain

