After the MRI, the subject will be presented with a series of images. They will then determine which of the images they saw while completing the tasks in the MRI. This task measures how well subjects were attending to stimuli during the brain scan.

Visit 3

Participants will take part in the VR task with the Oculus Quest VR headset. We will fit the headgear to the child and ensure that it is comfortable. Subjects will remain seated while interacting with the virtual world and use hand-held controls to move or control objects. Subjects can turn their head to look in any direction in the virtual world. Using state-of-the-art 'Oculus Touch' hand-held controllers that react to hand movements, the user will be able to move and interact with virtual objects and characters. Headphones play auditory stimuli.

Children will first explore the virtual cafeteria for three minutes to allow them to understand hand controls and become acquainted with the environment before starting the task scenarios. They may ask questions and talk with investigators during this time, who will ensure that subjects are able to use controls and move around in the environment properly.

The virtual environment is a school cafeteria setting. Following practice, participants will take part in three scenarios in the school cafeteria. Each scenario will last up to two minutes. In two scenarios, after the subject hears the school bell ring, the goal is to place trash on their cafeteria tray and take the tray to the trash. In a third scenario, the subject is directed to clean up the mess at their table. Once the task is complete, the scenario will be complete. In each scenario, virtual characters will populate the environment to make it more realistic, including some characters (students) who will also be returning their trays. However, the social environments will differ, and each scenario includes a virtual counterpart that interferes with the goal.

After each scenario, children will remove the headset and complete questions via electronic tablet. First, they will complete our **VR Perspective Taking Scale**, which assesses how well they understand the virtual counterpart's perspective. Next, they will complete a question for the **Acknowledgement of Other Perspective Scale**, which reflects the relative importance given to the perspective of the participant and the virtual counterpart.

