They will also complete a **Post-scenario Survey** regarding how they interpreted the intentions of the virtual counterpart (Were any of the characters trying to be nice to you? Were any of the characters trying to be mean to you?) and real-life responses (Would you be mad if this happened in real life? Would you try to hit other characters if this happened in real life?). Responses will be provided on a continuous sliding scale from 0 to 100 with labeled endpoints. We will also quickly assess current mood state (happy, sad, stressed, frustrated, calm) on sliding scales and complete the **Simulation Sickness Questionnaire** and a **VR Usability Survey**.

Following completion of each scenario, subjects will then experience the scenario again. Each subject will be randomly assigned to the (a) Alternate Perspective or (b) Control Perspective. In the Alternate Perspective condition, participants will experience the scenarios again from the virtual counterpart's perspective within the VR system. The Control Perspective will repeat the initial interaction from the same perspective. After each scenario, participants will answer questions identical to those after initial scenarios: the **VR Perspective Taking Scale** and the **Acknowledgement of Other Perspective Scale**, as well as questions about character intent, real-life responses, mood, the **Simulation Sickness Questionnaire**, and **VR Usability**.

If errors with the VR technology are observed, subjects may restart the scenarios and subsequent surveys.

Parents will also once again complete the Indiana Institute of Biomedical Imaging Sciences (IIBIS) **MRI Safety Screening Form** and the **Medication Log**.

Participants will be instructed about the MRI task and will briefly practice again. Participants will then undergo an MRI scan for about 1 hour. This scan may not be performed if the previous scan (at Visit 2) was not completed successfully. This scanning session will be identical to Visit 2, including an anatomical scan and functional scans in which participants will see images of painful and non-painful actions, under conditions where they are told to imagine scenes happening to themselves or the virtual counterpart, as well as the emotional face task.

After the scan, participants will be presented with images and asked to identify which ones they remember from the MRI scan.

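### The two VR scales are rated after all three initial scenarios, but the baseline is defined by the first rating only; if all initial scenarios precede any replay, the mean of the three is a better covariate for the same endpoint.

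*Combined protocol and SAP*

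**What the plan says.** - **Ratings collected.** Section 7.0 (Visit 3) says that "participants will take part in three scenarios in the school cafeteria", with both VR scales completed after each. After the replays, "After each scenario, participants will answer questions identical to those after initial scenarios". Each child thus gives three initial and three post-replay ratings on each scale.
- **Baseline and endpoint.** Section 3.0 defines the change score for both scales from one baseline rating, taken after the first scenario, to one endpoint rating, taken when all VR is finished.
- **Primary test.** Section 12.0 fits a mixed model to the post-treatment scores, with pre-treatment scores, time and time-by-condition among the regressors. From it, "we can both test for the primary endpoint (change at end of Scenario 3"; trends over time are examined as well. Section 12.0 does not say which pre-treatment rating enters, so the Section 3.0 definition is the only one available.
- **Power.** Section 12.0 claims 80% power at the two-sided 5% level for an ANCOVA comparison of the arms, 20 children in each, with the pre/post correlation set at 0.6. The difference to be detected is "an effect size of 0.73 (observed for the meanness rating in the preliminary study".
- **Order at Visit 3.** Section 5.0 and the Section 8.0 calendar put the initial scenarios and their assessments first, and the assigned-condition scenarios after them. Section 7.0 introduces the replay as coming after each scenario is completed, which could also mean scenario, replay, next scenario, replay.

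**The concern.** In an ANCOVA-type analysis, the baseline covariate helps only as far as it predicts the endpoint. A single rating carries the child's general level plus whatever is particular to that rating. The Acknowledgement of Other Perspective scale has one scenario-specific question per scenario, so its baseline under Section 3.0 is one answer about one scenario. That scenario need not be the one rated at the end.

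With 20 completers per arm and power planned at 80%, there is little margin. The two further initial ratings are already being collected. If they are true pre-treatment measurements, leaving them out of the adjustment gives up precision without a stated reason.

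**Working it through.** **Inputs from Section 12.0.** n = 20 per arm; effect d = 0.73 in units of the SD of a single rating; pre/post correlation 0.6; two-sided alpha 0.05.

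**Assumptions not in the documents.** All ratings have the same variance (set to 1). Each initial rating correlates 0.6 with the final rating. The initial ratings correlate with each other at r, shown for 0.6 to 0.9.

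**Step 1: the plan's own figure.** The residual SD after adjustment for one baseline rating is sqrt(1 − 0.6²) = sqrt(0.64) = 0.80. The adjusted effect is 0.73/0.80 = 0.9125, and the noncentrality is 0.9125 × sqrt(20/2). The noncentral t gives power of 80.3% with 38 df and 80.2% with 37 df (one df for the covariate). The stated 80% is reproduced.

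**Step 2: same endpoint, mean of three initial ratings as covariate.** The mean has variance V = (1 + 2r)/3 and covariance 0.6 with the final rating. The residual variance is 1 − 0.36/V. Power uses 37 df.

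| r | V | Residual variance | Residual SD | 0.73/SD | Power |
|---|---|---|---|---|---|
| 0.6 | 0.733 | 0.509 | 0.714 | 1.023 | 88.3% |
| 0.7 | 0.800 | 0.550 | 0.742 | 0.984 | 85.8% |
| 0.8 | 0.867 | 0.585 | 0.765 | 0.955 | 83.6% |
| 0.9 | 0.933 | 0.614 | 0.784 | 0.931 | 81.8% |

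A simulation of 4,000 trials at r = 0.6 gave 87.2% for this analysis and 78.5% for the single baseline, the same gap within simulation error.

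**Step 3: when the gain disappears.** Let the first initial rating correlate 0.6 with the endpoint and the other two correlate c. The covariance of the mean with the endpoint becomes (0.6 + 2c)/3. The mean is no better than the first rating alone when (0.6 + 2c)/3 = 0.6 × sqrt(V), that is, c = (1.8 × sqrt(V) − 0.6)/2. This gives c = 0.47, 0.50, 0.54 and 0.57 at r = 0.6, 0.7, 0.8 and 0.9. At r = 0.9 a small shortfall below 0.6 removes the gain.

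**Step 4: averaging the post-replay ratings instead.** With the first-scenario baseline, the residual variance of the mean of three post-replay ratings is (1 + 2r)/3 − 0.36, where r is now the correlation among those ratings. At r = 0.6 / 0.7 / 0.8 / 0.9:

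- Full effect of 0.73 after every replay: power 95.7% / 92.3% / 88.5% / 84.3%.
- Effect building as 50%, 75%, 100% of 0.73 (mean 0.75 × 0.73 = 0.5475): 78.8% / 72.0% / 65.9% / 60.5%.

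The last-rating test stays at 80.2% in both cases.

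**The case against.** **Visit order.** If replays are interleaved with initial scenarios, the second and third initial ratings follow treatment. Adjusting for them could remove part of the effect, and only the first rating is a clean baseline. This objection stands as a condition on the change. Sections 5.0 and 8.0 both point to a blocked order, but Section 7.0 leaves room for doubt.

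**Size.** The plan reaches its stated 80%, and at r = 0.9 the gain is only 81.8 − 80.2 = 1.6 points. The documents give no correlation among the initial ratings and no reliability for either scale, so the larger gains cannot be promised. This also stands. On the other side, the added ratings include one on the scenario that is replayed last if the scenario order is kept, and that rating may predict the endpoint at least as well as the first.

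**Stronger readings that the documents do not support.**

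- A reader might infer that most of the outcome data go unused. All post-replay ratings enter the mixed model and the trend analysis. How much they contribute to the Scenario 3 contrast depends on the coding of time, which is not stated. With categorical time and complete data, the contrast rests in effect on the last rating. With linear time and equal weighting, the three ratings carry weights of −1/6, 2/6 and 5/6, and power is 84.3% (r = 0.6) to 81.3% (r = 0.9).
- A reader might infer that the primary contrast should be the average over the three replays, with power of 84% to 96%. That needs the full effect after the first replay, whereas Section 12.0 includes time-by-condition to allow for improvement during treatment. It also changes the question from the effect of the completed intervention to an average that includes partial exposure.

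**Conclusion.** The point holds for the baseline, not for the endpoint. Two of the three initial ratings on each VR scale are left out of the baseline definition. Under the equal-correlation assumptions, including them raises power by 1.6 to 8.1 points (from 80.2% to between 81.8% and 88.3%). The endpoint, the comparison and the data collected stay the same.

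The result rests on three things: a blocked order at Visit 3, an assumed range of correlation among the initial ratings, and added ratings that predict the endpoint about as well as the first. The single late endpoint is a legitimate choice, and the plan's 80% is correct on its own inputs. This is a worthwhile gain in precision rather than an error that threatens validity. It concerns the two VR scales only, not the fMRI outcome.

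**What to change.** 1. Reconcile the Visit 3 description in Section 7.0 with Sections 5.0 and 8.0, so that it is clear whether all initial scenarios are completed before any replay.
2. If they are, state in Sections 3.0 and 12.0 that the pre-treatment covariate for each VR scale is the mean of the three initial ratings, and keep the end-of-Scenario-3 endpoint. If the order is interleaved, keep the first-scenario baseline.
3. State in Section 3.0 which baseline the descriptive change-score effect size uses. Its standard deviation, and so the reported Cohen's d, depends on that choice.
4. State in Section 12.0 whether time is categorical or linear, and correct the mention of two conflict scenarios where Section 7.0 has three.
5. If wanted, add the average condition effect over the three replays as a prespecified secondary contrast. It should not replace the primary.

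The cost is a few sentences and one covariate definition, with no new data or visits. The choice should be fixed before outcome data are seen by arm.
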